IVFE reduction (IFER) during the administration of neonatal parenteral nutrition will lead to a significant decrease in the rate of rise of direct bilirubin (mg/dL/week) when compared to standard therapy.

Secondary Hypotheses

1. The time to development of PNAC, when present, will be longer with IFER when compared to standard IVFE therapy.
2. IFER will not be associated with a significant increase in failure to thrive (as assessed by growth parameters) or the development of essential fatty acid deficiency (EFAD) when compared to standard IVFE therapy.
3. Neurodevelopmental outcomes (NDOs), when assessed at 12 and 24 months of corrected gestational age, will be similar for those treated with IFER and standard IVFE therapy.

Specific Aims

1. To determine whether neonates and infants receiving PN with IFER (1 g/kg/day) will have lower rates of rise of direct bilirubin compared to those receiving standard IVFE therapy (3 g/kg/day)
2. To compare the time to development of PNAC in neonates and infants receiving PN with IFER (1 g/kg/day) compared to those receiving PN with standard IVFE administration (3 g/kg/day)
3. To determine if IFER results in normal growth and essential fatty acid (EFA) parameters by measuring weight, length, head circumference (weekly) and EFA profiles (every 2 weeks in the IFER group) during the treatment period.
4. To compare NDOs at 12 and 24 months of corrected gestational (± 2 weeks) age of those treated with IFER with those treated with standard IVFE doses using a combination of neurodevelopmental screening tools (e.g. Bayley Scales of Infant Development, MacArthur Communicative Development Inventory, etc.) aimed at capturing several developmental domains such as motor, cognition, speech and language, sensory, and behavior.

Study Definitions

Subjects will be considered “on treatment” from the time of randomization until 7 days after PN has been discontinued, but not to exceed a total of 84 days. Subjects will be considered “on study” until they complete their neurodevelopmental testing at 24 months corrected gestational age (± 2 weeks).

Study Design

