This is a multi-institution, prospective, randomized study evaluating IVFE dose reduction on the development of PNAC as a proxy measure of PNALD in neonates requiring prolonged PN. The definition of PNAC will be that used predominantly in the literature – a direct bilirubin level of ≥ 2 mg/dL, documented on two occasions 1 week apart, in patients who have required parenteral nutrition for more than 2 weeks. **Eligible neonates will be randomized into two treatment arms: standard IVFE administration (3 g/kg/day) or IVFE reduction (IFER) (1 g/kg/day).** A total of 60 subjects (30 subjects per arm) will be included in the study. The study will evaluate

short- and long-term outcomes of this strategy. In the short-term, infants will be followed for up to 12 weeks for the development of PNAC. If a subject's PN is discontinued before 12 weeks, and if they remain in the hospital, follow-up data will be collected for an additional 7 days but not beyond a total of 84 days. Only standard-of-care data will be collected during these 7 days. No procedures will be performed for the purpose of this study during these 7 days. In the long-term, subjects' neurodevelopmental outcomes will be assessed at 12 and 24 months corrected gestational age (± 2 weeks).

Primary outcome measure:

1. The rate of rise of direct bilirubin as a function of time (mg/dL/week) between the two groups over 12 weeks or until the subject has been off of PN for >7 days, whichever comes first.

Secondary outcome measures

1. Initial 12 week period:
 - a. The incidence of PNAC (direct bilirubin ≥ 2 mg/dL) and severe PNAC (direct bilirubin ≥ 4 mg/dL in subjects on parenteral nutrition for at least 2 weeks)
 - b. The time to development of PNAC and severe PNAC
 - c. The peak total and direct bilirubin levels
 - d. The incidence of EFAD
 - e. Adequacy of growth as evaluated by z-scores for weight, height, and head circumference
 - f. Other safety measures assessed during the initial 12 week period will include adverse events (e.g., episodes of sepsis and catheter-related blood stream infections).
2. Long-term follow-up:

Neurodevelopmental assessments will include:

 - a. At 12 months corrected gestational age (± 2 weeks):
 - i. Bayley Scales for Infant and Toddler Development (BSID-III)
 - b. At 24 months corrected gestational age (± 2 weeks):
 - i. Bayley Scales for Infant and Toddler Development (BSID-III)
 - ii. MacArthur-Bates Communicative Development Inventories (CDI)

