 - iii. Brief Infant Toddler Social Emotional Assessment (BITSEA)
 - iv. Gross Motor Function Classification System (GMFCS)
 - v. Behavioral Assessment System for Children-Second Edition (BASC2)

Study Arms:

[figure not shown]
Study Arm 1 (Standard IVFE dosing): Subjects in the standard IVFE dosing arm (3 g/kg/day) will be on treatment for a total of 12 weeks or until the subject has been off of parenteral nutrition for >7 days, or if they are discharged from the hospital, whichever comes first.

Study Arm 2 (IFER dosing): Subjects in the IFER dosing arm (1 g/kg/day) will be on treatment for a total of 12 weeks or until the subject has been off parenteral nutrition for >7 days, or if they are discharged from the hospital, whichever comes first.

All subjects will be maintained at their assigned dosing regimen for the duration of the treatment period (12 weeks) or until they are transitioned off of PN for >7 days, are discharged or until the direct bilirubin is ≥ 2.5 mg/dL for 2 consecutive weeks, whichever occurs first. Data will be collected for the duration of the study for those subjects who remain on parenteral nutrition for the full 12 weeks. For those who transition off of PN prior to the end of the 12 week period, data will be collected for 7 days after termination of PN if the subject remains in the hospital. The clinical course of these subjects who wean off PN prior to 12 weeks will continue to be monitored according to standards of practice. If serum direct bilirubin reaches a level of ≥ 2.5 mg/dL for 2 consecutive weeks during the course of the treatment, subjects will be transitioned to an IVFE dose of 1 g/kg/day three days per week. Those who remain cholestatic at the termination of their treatment period will be evaluated on a monthly basis for the persistence or resolution of cholestasis. This will be done by obtaining monthly liver function tests and bilirubin fractions for 6 months.

Overview of Study Design:

Study Design

Inclusion Criteria

Study subjects will be neonates and infants who are ≥ 28 weeks corrected gestational age at the time of enrollment who are parenteral nutrition naïve (<72 hours of PN exposure prior to randomization) and whose direct bilirubin has never been >2 mg/dL with at least one of the following diagnoses:

1. Meconium ileus and peritonitis
2. Gastroschisis
3. Omphalocele >4 cm in diameter or with liver herniated outside of the abdominal cavity

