1. If TG are <250 mg/dL: restart IVFE at 50% of previous dose
2. If TG are ≥250 mg/dL: continue to hold IVFE infusion and repeat TG level every 48 hours until <250 mg/dL. If IVFE is held for ≥7 days with continued TG levels ≥250 mg/dL, restart IVFE at 0.5 g/kg/day

Essential Fatty Acid Deficiency (EFAD)

The detection of EFAD will be assisted by a biochemist and expert in the area of lipid biology.

The IVFE dose will be adjusted if subjects develop EFAD. EFAD will be defined by the development of any of the following:

1. Clinical evidence of EFAD deficiency (i.e. scaly skin)^{31,32}
2. Triene:tetraene ratio of >0.20
3. Arachidonic acid (ARA), (EPA) and/or docosahexaenoic acid (DHA) levels below normal as defined by Mayo Laboratory reference ranges

In the presence of EFAD, the IVFE dose will be increased in 0.5 g/kg/day increments based on biweekly essential fatty acid profiles until resolved.

Cycled Parenteral Nutrition

Study subjects will not receive cycled parenteral nutrition (i.e. parenteral nutrition administered over less than 24 hours per day) during the study period, as cycled PN has been shown to decrease the development of PNAC and may represent a confounder.^{33,34}

Adjustment of Parenteral Nutrition if Inadequate Weight Gain Occurs

(Lipid Restricted Group Only)

Subjects with inadequate weight gain that cannot be attributed to other physiologic causes (e.g. low urine sodium, low hematocrit, insufficient respiratory support) will be managed according to the protocol described below.

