3. Weight, gestational age at the time of enrollment/randomization, and weekly thereafter
4. Inclusion diagnosis
5. Number of septic episodes according to standard definitions³⁸
6. Use of choleric medications
 - a. Ursodiol
 - b. Cholecystokinin
 - c. Phenobarbital
7. Nutritional data
 - a. Parenteral nutrition data
 - i. IVFE dose
 - ii. Dextrose infusion rate
 - iii. Total calories and % calories obtained via PN
 - b. Enteral nutrition data
 - i. Total calories and % calories being obtained via enteral route
 - ii. % calories obtained via breast milk
8. Growth parameters (whenever possible, obtain all growth measurements on the same day of the week)
 - i. Weight (with z-score) weekly (every 7 days ± 2 days)
 - ii. Height (with z-score) weekly (every 7 days ± 2 days)
 - iii. Head circumference (with z-score) weekly (every 7 days ± 2 days)
9. Additional safety data to be obtained from human subjects is summarized below, indicating any key differences in frequency of monitoring between the two groups:

Laboratory Parameter	Frequency (+24 hours)*
Fractionated bilirubin panel (includes total, indirect, and direct bilirubin)	One time weekly (Monday)
Serum bile acids (total)	One time monthly (every 4 th Monday on treatment)

Point of care or serum glucose measures	- Daily for the first 5 days of PN, then twice weekly (Monday, Thursday) - Confirmatory test if serum glucose is >150 mg/dL on electrolyte panel
Serum Triglycerides	One time weekly (Monday)
Essential Fatty Acid Profile	IFER Group: Every 2 weeks (Thursday) Standard Group: At the time of restriction of IVFE to 1 g/kg/day three days per week, then every 2 weeks (Thursday)
Comprehensive metabolic panel	Twice weekly (Monday, Thursday)
Magnesium level	Twice weekly (Monday, Thursday)
Phosphorus level	Twice weekly (Monday, Thursday)
Complete blood count	One time weekly (Monday)

* Lab draw volumes will be below each institution's daily limits

Definition of Sepsis

Sepsis will be defined in a standard manner using the following criteria (**Table 2**):³⁸

The presence of at least two of the following four criteria ***in the presence of or as a result of suspected or proven infection***:

1. Core temperature of >38.5C or <36C

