These measures will be compared between the two treatment groups using a linear mixed model.

3. Incidence of PNAC, severe PNAC, and EFAD

The number of occurrences of each of these outcomes will be compared using either a Poisson regression model or a negative binomial model if the variance in these counts is greater than expected for a Poisson distribution. We will also include the time on TPN as an offset, so that we can compare the rates of occurrence of each of these outcomes for the two treatment groups. These regression models will be adjusted for the covariates such as development of sepsis, average IVFE dose, and percentage of enteral feeds.

4. Adequacy of growth as evaluated by z-scores for weight, height and head circumference

The z-scores for each of these measures will be compared between the two treatment groups using a linear mixed model. For normally growing infants, we would expect that there would not be a trend in z-scores because we would expect them to maintain their curve. However, for the subjects in this study, there may be a loss in z-score over time due to inadequate growth. The slopes of the changes in these z-scores over time will be compared between the two treatment arms. A random intercept will be included for each subject to allow for individual variability in average values as well as a random slope to allow for variability in the rate of change over time across subjects. Important covariates, such as gestational age (<32 weeks gestation vs. ≥32 weeks gestation) and birth weight will also be used as covariates in this analysis.

5. Neurodevelopmental Outcomes

Bayley Scales of Infant and Toddler Development (BSID-III):⁴⁵ Raw scores are converted to composite and subscale scores using age-standardized norms. Scale composite average internal consistency reliability coefficients range from .91 to .93 with subtest reliability ranging from .86 to .91. Validity-related studies indicate relatively high correlations (.72-.79) with the Wechsler Preschool and Primary Scale of Intelligence – Third Edition (WPPSI-III)⁵³ and with the Preschool Language Scale – Fourth Edition (PLS-4)(.71-.83).⁵⁴

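### EFAD rates are compared between arms, but laboratory EFAD is looked for every 2 weeks in IFER infants and in standard infants only at and after bilirubin-triggered restriction

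*Combined protocol and SAP*

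**What the plan says.** - **Hypothesis.** Secondary Hypotheses item 2 expects no significant increase with IFER in failure to thrive or "the development of essential fatty acid deficiency (EFAD) when compared to standard IVFE therapy".
- **Outcome.** Study Design, secondary outcome 1d: "The incidence of EFAD".
- **Analysis.** Planned Statistical Analysis, Secondary Outcome Measures item 3, models counts of PNAC, severe PNAC and EFAD by Poisson or negative binomial regression. Time on TPN is the offset, "so that we can compare the rates of occurrence of each of these outcomes for the two treatment groups". The covariates named are sepsis, average IVFE dose and percentage of enteral feeds.
- **Definition.** The EFAD section accepts any one of three criteria: clinical signs, "Triene:tetraene ratio of >0.20", or ARA, EPA and/or DHA below the laboratory reference range. The second and third need a fatty acid profile.
- **Schedule.** Data Collection item 9 gives the IFER group a profile every 2 weeks. For the other arm: "Standard Group: At the time of restriction of IVFE to 1 g/kg/day three days per week, then every 2 weeks (Thursday". The table is introduced as "indicating any key differences in frequency of monitoring between the two groups". Specific Aim 3 likewise mentions only "EFA profiles (every 2 weeks in the IFER group) during the treatment period".
- **Trigger.** Under Study Arms, at direct bilirubin of at least 2.5 mg/dL for 2 consecutive weeks, "subjects will be transitioned to an IVFE dose of 1 g/kg/day three days per week".
- **Other uses of EFAD.** It is a time-varying covariate in the between-arm neurodevelopmental model, one of three IFER-related predictors of neurodevelopment, and an expected adverse event (Monitoring for Adverse Events, item 4).

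**The concern.** A standard infant who is never restricted has no scheduled profile, so laboratory EFAD cannot be found in that infant by schedule. The infant still adds time on TPN to the denominator, and that time is counted as free of laboratory EFAD. None of the named covariates records whether an infant was tested. The six-monthly data collection does not fill the gap, because it takes profiles only where local practice provides them.

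The standard-arm profiles that do exist come from infants with raised bilirubin. After the first one they describe the restricted regimen (1 g/kg x 3 days = 3 g/kg/week, against 1 g/kg x 7 days = 7 g/kg/week at the assigned IFER dose). They say little about standard dosing.

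EFAD is the named safety question of lipid reduction. For the laboratory criteria, the planned rate ratio cannot answer it.

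**Working it through.** The plan gives no EFAD rate, margin or power, so there is no stated figure to reproduce. The check asks how unequal the testing would be and what that does to the comparison.

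**1. Scheduled profiles, IFER.** 12 weeks / 2 = about 6 per infant; 30 x 6 = 180.

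**2. Fraction of standard infants ever profiled.** Inputs from Sample Size Determination: standard-arm means 0.55, 1, 1.5 and 2 mg/dL at weeks 0, 4, 8 and 12; SD 1; correlations 0.5, 0.354 and 0.25 at lags of 4, 8 and 12 weeks. Weekly values were simulated with means interpolated.

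Assumptions: correlation at shorter lags set in two ways (0.707 x 2^(-lag/8), or 0.5^(lag/4) up to 4 weeks); normal or lognormal values; with and without a baseline limit of 2 mg/dL. That makes eight settings. The event is two consecutive weekly values of at least 2.5 mg/dL.

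| Result for standard infants followed 12 weeks | Range over settings |
|---|---|
| Ever reach the trigger, normal | 26-33% |
| Ever reach the trigger, lognormal | 21-27% |
| Reach it by week 8 | 9-15% |
| Median trigger week, among those who reach it | 8-10 |
| Profiles per standard infant | 0.5-0.9 |
| Profiles per profiled standard infant | 2.3-2.9 |

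In total, 30 x 0.515 = 15 to 30 x 0.884 = 27 standard-arm profiles are expected, against 180. Between 67% and 79% of standard infants have none. Infants who leave PN early (the plan allows 33% attrition) lower the tested fraction further.

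**3. Effect on the ratio.** Let q be the chance of detecting EFAD in a tested infant, equal in both arms, and f the fraction of standard infants tested, with testing unrelated to risk. Apparent ratio = q / (q x f) = 1/f. For f = 0.33 this is 3.0; for f = 0.21 it is 4.8.

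**4. Chance of a false significant difference.** Two-sided Fisher test at 0.05, 30 per arm, by exact binomial enumeration of q against q x f. This is a simple stand-in for the planned adjusted model.

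| q | f = 0.21 | f = 0.31 | f = 1 (equal testing) |
|---|---|---|---|
| 5% | 0.24% | 0.21% | 0.15% |
| 10% | 4.2% | 3.2% | 0.9% |
| 26% | 45% | 32% | 2.6% |

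**5. Which row is plausible.** The 26% is 8/31 from the single-center prospective study in the Background, which used a different regimen and an EFAD cut-off of 0.05. Two statements lie closer to this trial. The Background reports no clinical or laboratory EFAD in the reduced arm of the randomized pilot, at this trial's IFER dose. Potential Confounding Variables calls EFAD very rare in the coordinating university's experience with IFER. Both point to the low rows. Neither settles the risk under the third criterion, which is broader than a triene:tetraene ratio.

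**The case against.** **The asymmetry is deliberate and disclosed.** This stands. A reader might infer that the sampling schedule is itself a mistake. The documents do not support that: the table announces the difference, and Aim 3 describes profiles in the IFER group only. The error lies in using that schedule for a between-arm rate.

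**EFAD is rare at this dose.** This largely stands and limits the harm. A reader might infer from the 26% row that the trial will probably declare a false EFAD excess. That rate comes from another regimen and definition. At 5% risk, false significance is about 0.2%, against 0.15% with equal testing.

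**Standard dosing will not cause EFAD, so few cases are missed.** If so, the bias shrinks. The documents do not establish it. The hypertriglyceridemia rules allow lipid to be held or reduced in either arm, with no profile scheduled for standard infants.

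**The bias works against the sponsor's hypothesis.** For the laboratory criteria this is the likely direction, and a finding of no excess would not be produced by it. The estimate would still be uninterpretable.

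**Clinical EFAD can be seen in both arms, so compare that instead.** This stands only in part. IFER infants are profiled and their dose is adjusted for EFAD, possibly before skin signs appear; unrestricted standard infants are not screened. The care team is also unblinded. A clinical comparison therefore needs a caveat.

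**Conclusion.** The concern holds. As written, the EFAD rate ratio confounds treatment with testing. About 21-33% of standard infants followed for 12 weeks would ever be profiled, given the plan's bilirubin assumptions and the interpolation above. The apparent ratio of about 3-5 further assumes equal true risk, equal detection per tested infant and testing unrelated to risk. Tested standard infants are cholestatic, mostly on less lipid and profiled fewer times, so these conditions will not hold exactly, and the figure is neither an upper nor a lower bound.

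The main harm is a biased estimate that cannot be interpreted. The same unequal ascertainment reaches the neurodevelopmental models and the adverse-event count. EFAD is a secondary outcome with no stated power, and the plan offers such outcomes only as a basis for trends. The primary outcome is unaffected. The change should be made, and it is cheap.

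**What to change.** 1. **Secondary Outcome Measures item 3.** Remove laboratory EFAD from the between-arm regression. Proposed text: *Laboratory EFAD will not be tested between arms. In the IFER arm it will be reported as infants with EFAD over infants with at least one profile, with an exact 95% CI and the number of profiles. Standard-arm profiles at and after restriction will be listed separately, with their own denominator and no test.*
2. **Secondary hypothesis 2 and outcome 1d.** Align both with Aim 3: laboratory EFAD is described in the IFER arm. Clinical EFAD may be shown in both arms, with this caveat in the hypothesis and outcome text: *assessment is unblinded and IFER doses are adjusted on profile results, so this compares the strategies as monitored.*
3. **Neurodevelopmental Outcomes.** Drop the EFAD covariate from the between-arm model. Analyse EFAD as a predictor only among infants with at least one profile, which keeps the standard infants who were tested.
4. **Expected adverse events, item 4.** Add the same caveat on unequal monitoring.

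Precision of the IFER description (exact limits): 0/30 gives an upper 95% limit of 1 - 0.025^(1/30) = 11.6%; 0/20 gives 16.8%; 3/30 gives 2.1-26.5%.

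The cost is wording, with no new assays. The price is that no between-arm claim on laboratory EFAD can be made. If that claim is wanted, both arms need the same profile schedule: about 180 - 27 = 153 to 180 - 15 = 165 further profiles if every infant stays 12 weeks, and fewer with attrition.

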Subject's family members, the statistical team and those administering the neurodevelopmental tests will be blinded to treatment assignment. Blinding of families and those evaluating neurodevelopmental outcomes is particularly important as these are subjective assessments which we do not want to be biased by the treatment assignment. Adequacy of blinding will be assessed at the end of the initial 12 week treatment period by asking parents which treatment arm they believe the subject has been assigned to. Assessment of the adequacy of blinding will be performed and changes made if blinding of parents is deemed to be suboptimal. It is not possible to blind the inpatient care team and the investigators as the remainder of the PN formulation (dextrose, protein) must be adjusted to deliver adequate caloric needs to the subjects based on their IVFE treatment assignment. The lack of blinding during this phase of the study will not influence the short-term outcomes as they are discrete measurements that cannot be biased by subjectivity.

Standardization of Parenteral Nutrition Across Study Centers

The following guidelines for parenteral nutrition administration have been established to provide uniformity among study sites. Each site will follow these guidelines.

Energy

Total caloric delivery will range between 100-120 Kcal/kg/day when PN is the only source of calories
Total non-protein caloric delivery will not exceed 100 Kcal/kg/day when PN is the only source of calories

Carbohydrate

Dextrose infusion rate (DIR) will be increased in the following manner, provided there is no aberration in the serum glucose levels:

Day 1	DIR 4-8 mg/kg/min
Day 2 and beyond	Advancement of DIR by 1-2 mg/kg/min per day to a goal of 11-18 mg/kg/min

	For study subjects 0-30 days old the maximum DIR will be 16 mg/kg/min For study subjects >30 days old the maximum DIR will be 18 mg/kg/min
--	---

If hyperglycemia develops (defined as serum glucose >150 mg/dL), subjects will be managed in accordance with standard guidelines²⁸

1. Confirmatory point of care glucose test performed
2. If confirmatory glucose >150 mg/dL, the DIR will be reduced daily in increments of 1-2 mg/kg/min as tolerated until the serum glucose normalizes
3. Insulin will only be administered if hyperglycemia has not been controlled by adjusting the DIR

Protein

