5. Moderate undernutrition (decreased in z-score by ≥ 2 standard deviations) to severe undernutrition (decreased in z-score by ≥ 3 standard deviations)
6. Thrombophlebitis
7. Hypercoagulopathy
8. Thrombocytopenia (platelet count <50 k/mm³)

Determination of Relatedness:

Generally, the definition of an adverse event could include worsening of a pre-existing condition and investigators could be asked to make the distinction between exacerbation of a pre-existing condition and an event related to the study protocol when recording and reporting adverse event. However, due to the nature of the population being studied, the typical effects of the underlying condition may not yet be present at Baseline.

Standard IV lipid dosing compared to IV lipid minimization for the prevention of PNAC/PNALD

Based on clinical information, an adverse event will be determined by the site PI to be definitely not related, unlikely to be related, possibly related, definitely related or insufficient information to Intralipid® 20% administration or other study procedures. Usual effects from the subject's condition that are considered by the site PI to be not related to Intralipid® 20% administration or other study procedures will be noted in the subjects' medical records but will not be recorded or reported as an adverse event for this study. Examples include emesis, reflux and pain due to an expected surgery/procedure.

Adverse Event Reporting

All adverse events that occur from the time of consent until the patient completes 12 weeks of TPN or has been off TPN for 7 days, whichever comes first will be assessed for expectedness and relatedness and recorded in the subject's study binder.

Only adverse events considered to be possibly related to Intralipid® 20% administration or other study procedures will be reported to the sponsor, the IRB, the FDA, and the DSMB.

Severe Adverse Event Reporting

Although no serious adverse reactions are anticipated, study participants will be monitored, and any such events will be recorded and reported to the appropriate regulatory committees. These include:

- Death while on the study
- Any study-related event that prolongs hospitalization
- Any study-related event that requires an operative procedure

Mortality will be defined as a death occurring at any time during the child's admission to the hospital. The cause of death, autopsy findings and whether the subject was on study drug at the time of death will also be recorded.

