All adverse events will be graded as follows in their relation to IFER: definitely not related, unlikely to be related, possibly related, definitely related or insufficient information. All cases rated as possibly or definitely related will be defined as an SAE. These SAEs will be reported to the University of Michigan Sponsor-Investigator within 48 hours. The site PI will be contacted immediately and the case will be evaluated for reporting to IRB, FDA and study termination, if deemed necessary. Each clinical site will report SAEs to their local IRB as per their standard reporting policy. As per 21 CFR 312.32(c), the sponsors will also notify FDA and all participating investigators in an IND safety report of any adverse experience associated with the use of the drug that is both serious and unexpected.

Data Safety Monitoring Board

An independent data safety monitoring committee will be established to monitor the study for safety and to determine if a statistical difference has been achieved between the two groups for the primary outcome measure at interim data analyses. The data safety monitoring committee will review the data at the halfway point of the study to assess the safety and efficacy of the study to that point. If safety issues are revealed the study investigators and each site's IRB will be notified immediately. The data safety monitoring committee will also ensure that adverse events are promptly reported to the FDA, and all participating investigators will be notified as well of any adverse experience associated with the use of the drug that is both serious and unexpected.

Sample Size Determination

The sample size was calculated for the primary outcome (rate of rise of direct bilirubin) using previously published data as well as our clinical experience.^{22,23} We have assumed that the mean bilirubin levels at baseline, 4 weeks, 8 weeks and 12 weeks in the standard dosing group (2-3 g/kg/day) will be 0.55 mg/dL, 1 mg/dL, 1.5 mg/dL and 2 mg/dL corresponding to a slope of 0.125 mg/dL/week over 12 weeks. The standard deviation of the bilirubin measures at each of these four time points is 1. Likewise, we have estimated that the mean bilirubin levels at baseline, 4 weeks, 8 weeks and 12 weeks in the minimization group (1 g/kg/day) will be 0.45 mg/dL, 0.5 mg/dL, 0.45 mg/dL and 0.5 mg/dL (a slope of roughly zero). The standard deviation of the bilirubin measurements at

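### Adverse event reports to the sponsor and DSMB depend on a relatedness rating by an unblinded site investigator, so the arm comparison of events not collected elsewhere can be distorted

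*Combined protocol and SAP*

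**What the plan says.** Secondary outcome 1f makes adverse events a safety outcome of the trial: "Other safety measures assessed during the initial 12 week period will include adverse events", with sepsis and catheter-related bloodstream infection as its examples. The Data Safety Monitoring Board section adds: "The data safety monitoring committee will review the data at the halfway point of the study to assess the safety and efficacy". It does not define what data the committee receives for that review.

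Four provisions decide which events travel beyond the site.

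- **Who judges.** Determination of Relatedness: "an adverse event will be determined by the site PI to be definitely not related", or one of four other grades, with respect to Intralipid or study procedures.
- **What that person knows.** Blinding: "It is not possible to blind the inpatient care team and the investigators".
- **What is recorded.** Usual effects of the infant's condition that the site investigator considers unrelated are noted in the medical record but "will not be recorded or reported as an adverse event for this study". The examples are vomiting, reflux and procedural pain. Other adverse events in the reporting window go into the site's study binder.
- **What is forwarded.** Adverse Event Reporting: "Only adverse events considered to be possibly related to Intralipid® 20% administration or other study procedures will be reported to the sponsor". The sentence also names the IRB, the FDA and the DSMB as recipients.

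Severe Adverse Event Reporting lists death without a relatedness condition. Its two other items, prolonged hospital stay and an operation, count only when study-related. The section then grades events again, this time by their relation to IFER, and treats both possibly and definitely related cases as SAEs to be sent to the sponsor-investigator within 48 hours.

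**The concern.** A randomised comparison of adverse events is protected from bias when events are counted the same way in both arms, whatever anyone believes about cause. Here a causal opinion comes between the event and the report, and the person giving it knows the arm. If investigators attribute events more readily in one arm, the reports can show a difference that does not exist or conceal one that does.

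The plan's defence of the open design does not cover this. It says: "The lack of blinding during this phase of the study will not influence the short-term outcomes", on the ground that those outcomes are discrete measurements. A five-level opinion about cause is not a measurement of that kind.

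Unequal attribution is plausible given the wording. One scale asks about giving Intralipid, which fits harm from more lipid more naturally than harm from less. The other asks about IFER, the assigned regimen of one arm only. At stake is how far the DSMB's halfway safety review and outcome 1f can be relied on for events whose only stated route to the sponsor and committee is the adverse event report.

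**Working it through.** The plan gives no adverse event rate or attribution rate, so there is no figure to reproduce. The check has two parts.

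**1. Which safety information passes through the filter**

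| Information | Where collected or analysed | Depends on the relatedness rating? |
|---|---|---|
| Septic episodes | Data Collection item 5; rates compared by Poisson or negative binomial regression under Planned Statistical Analysis | No |
| Death | Listed as serious without condition; mortality examined as a secondary outcome under Potential Confounding Variables | No |
| Growth z-scores | Weekly; slopes compared by arm | No |
| Glucose, triglycerides, blood counts | Scheduled in both arms | No |
| Essential fatty acid deficiency | Own secondary outcome and analysis | No (profiles are scheduled from the start only in the IFER arm, a separate ascertainment issue) |
| Catheter-related bloodstream infection as such | Named in outcome 1f; no item under Data Collection | Yes, for reports to sponsor and DSMB |
| Catheter replacement, thrombophlebitis, hypercoagulopathy | Expected adverse events only | Yes |
| Unlisted events | Adverse event reports | Yes |
| Non-fatal serious events | Listed only if study-related | Yes |

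Of the eight numbered expected categories, four (hyperglycemia, hypertriglyceridemia, undernutrition, thrombocytopenia) are thresholds on variables measured on schedule in both arms, and fatty acid deficiency has its own analysis. Three remain exposed: line complications, thrombophlebitis and hypercoagulopathy.

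**2. What unequal rating could do (assumed rates)**

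Let n be the infants per arm, p the true risk of an event and q the share rated related. The expected number reported is n × p × q. The plan gives n = 30 per arm at full enrolment. At the halfway review n is about 15, if halfway means half of enrolment. Values of p and q are assumptions. The last column is the exact probability that a two-sided Fisher test at 0.05 is significant although the true risks are equal.

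| n per arm | p (both arms) | q, arm A v arm B | Expected reported | Fisher significant |
|---|---|---|---|---|
| 30 | 0.40 | 0.50 v 0.50 | 6.0 v 6.0 | 2.2% |
| 30 | 0.20 | 0.70 v 0.30 | 4.2 v 1.8 | 5.7% |
| 30 | 0.40 | 0.70 v 0.30 | 8.4 v 3.6 | 23.1% |
| 30 | 0.60 | 0.70 v 0.30 | 12.6 v 5.4 | 43.0% |
| 15 | 0.20 | 0.70 v 0.30 | 2.1 v 0.9 | 2.0% |
| 15 | 0.40 | 0.70 v 0.30 | 4.2 v 1.8 | 9.3% |
| 15 | 0.60 | 0.70 v 0.30 | 6.3 v 2.7 | 16.5% |

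For the third row: 30 × 0.40 = 12 infants with an event in each arm; 12 × 0.70 = 8.4 and 12 × 0.30 = 3.6.

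Masking works the same way. With true risks of 0.20 and 0.40 and attribution of 0.70 and 0.35, the reported risks are 0.20 × 0.70 = 0.14 and 0.40 × 0.35 = 0.14, so a true doubling disappears.

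With equal q the filter removes events but does not bias the comparison. The distortion depends wholly on the attribution gap, about which the documents say nothing.

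**The case against.** The strongest reply is that most of the safety comparison never touches the relatedness rating, as the first table shows. A reader might infer that the randomised safety comparison as a whole is lost; the documents do not support that.

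A reader might also infer that definitely related events never leave the site, since the forwarding sentence names only possibly related ones. Severe Adverse Event Reporting sends definitely related cases to the sponsor-investigator. What stands is that it states no route for them to the DSMB, and that neither section gives a route for cases rated as having insufficient information.

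Nor do the documents establish that the DSMB sees only filtered data. The forwarding sentence puts the DSMB beside the IRB and FDA, which reads as event reporting, and nothing limits the halfway review to forwarded reports. Equally, nothing promises the committee the unfiltered set. Monitoring and Follow Up of Subjects says that clinical complications are recorded, without saying that they reach the DSMB.

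The recording rules are not a clear contradiction either: the usual-effects exclusion can be read as defining what counts as an adverse event, and the next section as requiring all events so defined to be recorded. That reading still leaves the exclusion to an unblinded judgement.

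Finally, some bloodstream infections will be counted as septic episodes, because positive cultures qualify. This narrows the gap for catheter infection but does not close it: outcome 1f names it separately from sepsis.

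**Conclusion.** The point holds in a limited form. The plan states a rule, not merely a silence: adverse event reports to the sponsor and DSMB are confined to events that an unblinded investigator rates possibly related, and non-fatal serious events are listed only if study-related. For catheter-related bloodstream infection as such, catheter replacement, thrombophlebitis, hypercoagulopathy and unlisted events, the comparison resting on those reports can be distorted by knowledge of the arm.

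Direction and size cannot be determined from the documents. The figures above show only what an assumed gap would do; at about 15 per arm, expected reported counts are small and a spurious significant result is less likely than at 30. The conclusion assumes that adverse event reports are the main route by which these events reach the sponsor and DSMB, which the plan implies but does not state for the halfway review. The change is worth making as a cheap improvement.

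**What to change.** 1. Keep the expedited route for related events. In addition, send every adverse event recorded in the study binders, whatever its attribution, to the sponsor's database, and give the DSMB a by-arm table of them at the halfway review. Use that set for outcome 1f.
2. Reconcile Determination of Relatedness and Adverse Event Reporting with Severe Adverse Event Reporting. Use one object of attribution that applies to both arms (at present Intralipid or study procedures in one place, IFER in another), and state where possibly related, definitely related and insufficient-information cases go.
3. Apply the usual-effects exclusion through a list of events fixed in advance and used identically in both arms, in place of case-by-case judgement. Without this, tabulating the binder entries leaves the earlier filter in place, because excluded events never reach the binder.

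The cost is modest data management: entering events already assessed at the sites, one additional DSMB table, and a short clarification of the text. No treatment, visit or measurement changes.
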